5.4.4. Laboratory evaluations

The shift table will be used to summarize the baseline and post-baseline laboratory test results by worst clinical significance (normal, abnormal without clinical significance, abnormal with clinical significance), including hematology, blood biochemistry, coagulation function, stool routine, urinalysis, and thyroid function tests (T3, FT3, FT4, TSH). The post-baseline measurements of each subject are summarized according to the worst severity grades. Severity, in descending order: Abnormal with clinical significance, abnormal without clinical significance, normal, and not examined.

Based on the SS, the median values of alanine aminotransferase, aspartate aminotransferase, total bilirubin, γ -glutamyl transferase, and alkaline phosphatase from subjects with clinically significant abnormalities in alanine aminotransferase or aspartate aminotransferase tests post baseline will be plotted by visits.

All laboratory test results will be listed.

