3.1.1 Definition of clinically significant toxicity

1. Grade 4 hematological toxicity or Grade ≥ 3 thrombocytopenia with hemorrhage, Grade ≥ 3 neutropenia with fever and infection;
2. Grade ≥ 3 non-hematological toxicity (except for abnormal laboratory test parameters), hypertension, rash, diarrhea, nausea, and vomiting that cannot be controlled after symptomatic treatment;
3. Grade ≥ 3 abnormal laboratory test parameters that lead to medical intervention, hospitalization, or lasting for ≥ 7 days;
4. SHR-1210 interruption for > 14 days due to relevant toxicity (delayed administration in Cycle 1 or Cycle 2);
5. Apatinib interruption for > 7 days due to relevant toxicity.

3.1.2 Definition of subjects with incomplete tolerance evaluation:

During the observation period of tolerability, the dose of SHR-1210 is < 90% of the prescribed dose due to non-clinically significant toxicity (such as injection reactions).

Subjects who do not complete the tolerability evaluation will not be included in the overall number of subjects undergoing tolerability evaluations, and each dose group is required to have ≥ 10 subjects for the tolerability observation.

Exemption: If ≥ 7 subjects in a dose group do not develop clinically significant toxicity during the tolerability observation period, the dose group is considered to be tolerable and no new subjects will be enrolled into this dose group.

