Cohort 4. Non-squamous and non-small cell lung cancer with wild-type EGFR and ALK and with bTMB ≥ 1.54 muts/Mb or tTMB > 10 muts/Mb confirmed by central laboratory, and patients in the stage of a palliative treatment who have received no systemic treatment.

5. ECOG PS: 0-1;
6. Life expectancy ≥ 12 weeks;

7. Major organ functions must meet the following rules (not including the use of blood components or cell growth factors during screening):
 - Absolute neutrophil count $\geq 1.5 \times 10^9/L$;
 - Platelets $\geq 100 \times 10^9/L$;
 - Hemoglobin ≥ 9 g/dL;
 - Serum albumin ≥ 3 g/dL;
 - Thyroid stimulating hormone (TSH) \leq ULN (In the case of abnormalities, FT3 and FT4 levels should also be measured. If FT3 and FT4 levels are normal, the patient can be enrolled);
 - Total bilirubin \leq ULN;
 - ALT and AST $\leq 1.5 \times$ ULN;
 - AKP $\leq 2.5 \times$ ULN;
 - Serum creatinine $\leq 1.5 \times$ ULN or creatinine clearance ≥ 60 mL/min (using the standard Cockcroft-Gault formula, as shown in Appendix 3);
8. Female patients of a childbearing age who are not surgically sterilized should adopt a medically approved contraceptive measure (such as an intra-uterine contraceptive device, contraceptive pills or condoms) during the study treatment period and within 3 months after the end of the study treatment; female patients of a childbearing age who are not surgically sterilized must have a negative serum or urine HCG test result within 72 h prior to study enrollment, and must not be in the lactation period; male patients should be surgically sterilized or agree to use an appropriate contraceptive measure during the study period and within 3 months after the last dose of the study drug;
9. Patients must participate voluntarily, sign the informed consent form, have good compliance, and cooperate with follow-up visits.

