8 SAFETY EVALUATION

8.1 Adverse Events (AEs)

8.1.1 Definition of adverse event

An adverse event (AE) refers to any untoward medical occurrence in a study subject administered a medicinal product and which does not necessarily have a causal relationship with this treatment. For the specific period of AE collection in this study, please refer to Section 8.3. AEs include the following:

- 1) Worsening of pre-existing (prior to entering clinical study) medical conditions/diseases (including worsening symptoms, signs, or laboratory abnormalities);
- 2) Any new AEs: Any new adverse medical conditions (including symptoms, signs, and newly diagnosed diseases);
- 3) Clinically significant abnormal laboratory findings.

The investigator should record any AEs that have occurred in detail, including the description of the AEs and all relevant symptoms, time of occurrence, severity, causality with the study drugs, duration, measures taken, and final results and outcomes.

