13.4.4 Safety evaluation

Descriptive statistical analysis will be primarily used to analyze the adverse events, serious adverse events and adverse reactions in each dose group (the adverse reactions are defined as adverse events that are "definitely related, probably related, and indeterminable" to the study drug). Laboratory test results will describe the conditions that are normal before the study but become abnormal after treatment. The mean, standard deviation, median, minimum, and maximum of vital signs (blood pressure, pulse, body temperature, and respiratory rate) before and after single-dose administration will be respectively calculated by dose group.

Besides, irAEs, including immune-related pneumonitis, immune-related enteritis, immune-related thyroid dysfunction, immune-related nephritis and renal failure, and immune-related hypophysitis will be categorized and summarized using above summary analysis of AEs.

Laboratory parameters, ECG, the number and rate of laboratory parameters "changed from normal to abnormal" or "exacerbated", and abnormalities after the study and their clinical explanations will be tabulated.

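### Laboratory shift tables in SAP 5.4.4 use only clinical-significance categories, so worsening within a category is not counted and the protocol's tabulation of exacerbated parameters is only partly delivered

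*SAP*

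**What the plan says.** SAP 5.4.4 plans a shift table from baseline to the worst post-baseline result, "by worst clinical significance (normal, abnormal without clinical significance, abnormal with clinical significance"). It covers hematology, biochemistry, coagulation, stool, urine and thyroid tests. The same section fixes what worst means: "Severity, in descending order: Abnormal with clinical significance, abnormal without clinical significance, normal, and not examined". No CTCAE grade enters this ordering. The section's other outputs are by-visit plots of medians for five liver parameters, limited to subjects with a clinically significant ALT or AST abnormality after baseline, and a full listing of results.

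Protocol 13.4.4 makes two commitments on laboratory data. One is general: "Laboratory test results will describe the conditions that are normal before the study but become abnormal after treatment". The other is that "the number and rate of laboratory parameters 'changed from normal to abnormal' or 'exacerbated" will be tabulated. Neither document defines *exacerbated*, and the SAP does not use the word.

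Two other protocol sections matter here. Entry criteria in 5.1 admit some abnormal baselines, for example "ALT and AST $\leq 1.5 \times$ ULN". Section 8.1.1 counts as AEs both "Clinically significant abnormal laboratory findings" and the worsening of pre-existing conditions, "including worsening symptoms, signs, or laboratory abnormalities".

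**The concern.** A table with a single boundary between two abnormal categories can record only one kind of worsening in a value that was abnormal to begin with: crossing that boundary. Worsening on either side of it leaves the subject in the same cell. A value already in the top category at baseline cannot move up at all.

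The protocol promised a count of exacerbated parameters, and elsewhere it treats laboratory grade as meaningful. Its definition of clinically significant toxicity in 3.1.1 includes Grade ≥ 3 "abnormal laboratory test parameters that lead to medical intervention, hospitalization, or lasting for" at least 7 days, and the hematologic dose rules in 6.4 are set by grade. The planned laboratory table cannot be read on that scale.

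At stake is the descriptive safety report. Without a table built from measured values, graded laboratory abnormalities reach the summaries only through AE reporting. In an open-label study a value-based table would be a useful independent check on that reporting.

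**Working it through.** There is no planned figure to reproduce, because the documents attach no number to this table. The check is a comparison of text, followed by a small enumeration.

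**Commitment against delivery**

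| Protocol 13.4.4 commitment | What the SAP 5.4.4 table shows |
|---|---|
| Normal before, abnormal after | Shown, as normal to either abnormal category |
| Exacerbated | Shown only when the value moves from abnormal without to abnormal with clinical significance |
| Exacerbated within a category | Not shown |

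**How much worsening could be hidden**

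Take a test graded 1 to 4 and an abnormal baseline. The possible worsening moves are 1→2, 1→3, 1→4, 2→3, 2→4 and 3→4, six in all. A grade-based shift table shows all six. For the planned table, assume that clinical significance begins at some grade k. The documents give no such rule, so k is varied. A move is visible only if it starts below k and ends at k or above, so the number visible is (grades below k) × (grades at or above k).

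| Assumed start of clinical significance | Visible, any abnormal baseline | Visible, baseline Grade 1 only |
|---|---|---|
| Grade 2 | 1 × 3 = 3 of 6 | 3 of 3 |
| Grade 3 | 2 × 2 = 4 of 6 | 2 of 3 |
| Grade 4 | 3 × 1 = 3 of 6 | 1 of 3 |
| All abnormal values in one category | 0 of 6 | 0 of 3 |

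The last column is the more realistic case if baseline abnormalities are mostly mild. Protocol 5.2 points that way, since it excludes subjects whose prior-treatment adverse events (other than alopecia) have not returned to Grade 1 or below. The table counts kinds of move, not subjects; the documents do not give the frequency of each.

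**Weight of one subject**

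SAP section 5 sets all safety analyses by population. From planned numbers, one subject is worth:
- driver gene negative, at least 78 + 38 = 116 (cohorts 1 and 3, before adding Stage I subjects): at most 1/116 = 0.9 percentage points;
- driver gene positive, at least 38 (cohort 2): at most 1/38 = 2.6 points;
- cohort 4, 20 subjects: 1/20 = 5.0 points;
- apatinib 375 mg, 10–12 tolerability plus 10–12 PK subjects, so 20–24: 1/24 to 1/20, or 4.2 to 5.0 points.

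**Other value-based summaries in the SAP**

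Vital signs (5.4.5) have descriptive statistics by visit. ECG (5.4.6) has descriptive statistics and numeric cut-offs, such as a QTc of at least 500 ms. Laboratory data have only the liver plots, which are themselves restricted to subjects already flagged as clinically significant.

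**The case against.** The case against is substantial, and most of it limits the point.

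- **Graded laboratory severity is not absent from the report.** SAP 5.4.3 grades AEs by CTCAE v4.03, tabulates Grade ≥ 3 events, and repeats this for 250 mg against 375 mg. A reader might infer that no Grade 3–4 laboratory rate will be available. That is true only of the tables in 5.4.4.
- **AE reporting of laboratory values does not rest on clinical significance alone.** Protocol 8.1.1 makes worsening laboratory abnormalities AEs with no significance test, 8.1.3 asks that abnormal laboratory changes be recorded, and 8.2.3 sets numeric liver thresholds for SAEs. A reader might infer that one investigator's judgment filters the data twice; these sections do not support that. SAP 5.4.4 also does not say who assigns significance. The investigator is a reasonable inference, but not stated.
- **The primary endpoint is not touched.** The Stage I endpoint is incidence and severity of AEs and SAEs, analysed in SAP 5.4.3. The DLT analysis in 5.4.2 uses the toxicity definition. Neither draws on the shift table.
- **Some worsening is visible**, as the comparison shows, and the protocol promises no CTCAE-graded laboratory table.
- **The blind spot is narrower for some tests.** Total bilirubin must be at or below ULN at entry, so an eligible subject cannot start with it elevated.
- **A ten-subject denominator would overstate the effect.** SAP section 5 pools Stage I 250 mg subjects with Stage II cohorts, and the 375 mg group is planned with PK subjects as well.

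All of this stands. What it leaves is that AE tables contain only what was reported as an AE, that a listing is not a count or a rate, and that within-category worsening is counted nowhere in 5.4.4. The special-interest liver event is likewise identified by preferred term in SAP Appendix 2, with no stated derivation from the measured values.

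**Conclusion.** The point holds as a gap in descriptive safety reporting. The planned laboratory table delivers the normal-to-abnormal count and part of the exacerbated count; worsening within a category is missing. Depending on the unstated threshold for clinical significance, it would show 0 to 4 of the six possible grade-worsening moves, or 0 to 3 of three if baselines are confined to Grade 1. One missed subject would be worth about 4 to 5 percentage points in the smaller planned groups and under 1 point in the driver gene negative population.

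This rests on two assumptions: that some subjects enter with abnormal values, which the entry criteria permit but the documents do not quantify, and that significance follows a grade threshold, used only for the illustration. It does not extend to the Stage I primary endpoint, the DLT analysis or any efficacy conclusion. The change is worth making because it is cheap, is less dependent on judgment than the present categories, and completes a count that the protocol specifies.

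**What to change.** Add to SAP 5.4.4, for tests that can be graded numerically:

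- a shift table of baseline grade against worst post-baseline grade, using NCI-CTCAE v4.03 derived from the measured value and the local normal range, with high and low directions separate;
- counts and percentages of subjects with any post-baseline Grade ≥ 3, and of subjects who worsen by at least one grade from baseline, the latter stated as the definition of *exacerbated* for Protocol 13.4.4;
- presentation by the populations and cohorts of SAP section 5.

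Keep the present categories for stool and urine dipstick tests. The clinical-significance flag can stay in the listings. If grading proves impractical, the minimum is to define *exacerbated* in the SAP and count it.

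The cost is SAP wording and standard programming, which fits the SAP's own plan to finalise before database lock. Local normal ranges must be in the database. SAP 4.2.2 does not say that they are collected, so this should be confirmed first. No new subject assessments are needed.

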5.4.5. Vital signs

Vital signs will be summarized by visit using descriptive statistics for each population/cohort.

All vital signs will be listed.

5.4.6. 12-Lead ECG

Mean values of 12-lead ECG results will be taken at each visit. Examination items of ECG include: HR (beats/min), PR interval (ms), QT interval (ms), QTc (ms), and QRS (ms).

The baseline and worst grade post baseline or clinical significance will be summarized by shift table. Clinical significance includes normal, abnormal without clinical significance, and abnormal with clinical significance.

Measurements of each ECG variable at each time point will be analyzed using descriptive statistics.

ECG parameters measured at the study site will be summarized as follows:

- Maximum PR interval ≥ 300 ms
- Maximum QT interval ≥ 500 ms
- Maximum QTc interval (ms) (450-<480, 480-<500, ≥ 500)
- Maximum QTc interval ≥ 480 ms or increase > 60 ms from baseline

Related data will also be reported in listing.

5.4.7. ECOG PS

The baseline and highest ECOG PS post baseline for each population/cohort will be summarized using a shift table.

All ECOG PS will be reported in the form of listing.

5.4.8. Physical examination

Data of physical examination will be listed.

5.4.9. Other safety measures

Echocardiography results will be listed.

5.5. Pharmacokinetic Analysis

See independent PK analysis report.

5.6. Other Analyses

NA.

6. INTERIM ANALYSIS

NA.

8. APPENDIX

Appendix 1: Best overall response when confirmation of CR and PR required

Overall Response at First Time Point	Overall Response at Subsequent Time Point	Best Overall Response
CR	CR	CR
CR	PR	SD, PD, or PR ^a
CR	SD	SD (provided minimum criteria for SD duration met, otherwise, PD)
CR	PD	SD (provided minimum criteria for SD duration met, otherwise, PD)
CR	NE	SD (provided minimum criteria for SD duration met, otherwise, NE)
PR	CR	PR
PR	PR	PR
PR	SD	SD
PR	PD	SD (provided minimum criteria for SD duration met, otherwise, PD)
PR	NE	SD (provided minimum criteria for SD duration met, otherwise, NE)
NE	NE	NE

CR = complete response, PR = partial response, SD = stable disease, PD = progressive disease, and NE = not evaluable.

a: If a CR is truly met at first time point, then any disease seen at a subsequent time point, even the disease meeting PR criteria relative to baseline, makes the disease PD at that point (since disease must have reappeared after CR). Best overall response will depend on whether minimum duration for SD is met. However, sometimes CR may be claimed when subsequent scans suggest small lesions are likely still present and in fact the subject has PR, not CR at the first time point. Under these circumstances, the original CR should be changed to PR and the best response is PR.

Appendix 2: List of Preferred Terms for Special Interest Events

Special Interest Event	Classification	AE Preferred Term (coded as per v24.0)
Grade 4 amylase or lipase increased	Amylase increased	Amylase increased
Grade 4 amylase or lipase increased	Lipase increased	Lipase increased
Reactive capillary endothelial proliferation		Reactive capillary endothelial proliferation
Grade ≥ 3 infusion reaction		Infusion related reaction
Grade ≥ 2 diarrhea/colitis	Colitis	Colitis ulcerative
Grade ≥ 2 diarrhea/colitis	Colitis	Enterocolitis
Grade ≥ 2 diarrhea/colitis	Colitis	Colitis
Grade ≥ 2 diarrhea/colitis	Diarrhea	Frequent bowel movements
Grade ≥ 2 diarrhea/colitis	Diarrhea	Diarrhoea
Grade ≥ 2 uveitis		Uveitis
Grade ≥ 2 uveitis		Eye pain
Grade ≥ 2 interstitial pneumonia		Interstitial lung disease

Special Interest Event	Classification	AE Preferred Term (coded as per v24.0)
Hepatic enzyme abnormal		Hepatic enzyme abnormal
Other Grade ≥ 3 irAEs	Immune-mediated lung disease	Immune-mediated lung disease
Other Grade ≥ 3 irAEs	Pneumonia	Pneumonitis
Other Grade ≥ 3 irAEs	Immune-related hepatitis	Immune-mediated hepatitis
Other Grade ≥ 3 irAEs	Hepatic function abnormal	Hepatic function abnormal

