9.2 Infusion Reactions

As a fully humanized monoclonal antibody, SHR-1210 poses relatively lower risks of infusion reactions and prophylactic is therefore not required. Once an infusion reaction occurs, the infusion should be slowed or interrupted accordingly, and a supportive treatment should be given. Also, prophylactics should be given before further administrations. For acute infusion reactions (including cytokine release syndrome, angioedema, anaphylactic shock, allergic reactions, please refer to terms and criteria of NCI CTC AE v4.03), their relevant symptoms and signs usually occur during drug infusion or shortly after infusion, and usually disappear within 24 h after the infusion is completed. The signs and symptoms include: allergic reaction/hypersensitivity reaction (including drug-induced fever), coughing, chills, rigor, dizziness, headache, fatigue (weakness, somnolence), rash/peeling skin, pruritus/itching, arthralgia, myalgia, hypotension/hypertension, nausea, vomiting, diaphoresis, tachycardia, cancer pain, urticaria, dyspnea (shortness of breath), or bronchospasms. Any Grade 3 or 4 infusion reactions must be reported to the sponsor within 24 hours, and should be reported as SAEs if the criteria for SAE are met.

Management of allergic reactions should be based on the medical practice and guidelines of the study center. The treatment recommendations for infusion reactions are shown below for reference.

Table 9-1. Treatment recommendations for infusion reactions

CTCAE Grade	Clinical Symptoms	Clinical Management	SHR-1210 Treatment
Grade 1 (mild)	Mild and transient reactions;	Bedside observation and close monitoring until recovery. (Prophylactics are recommended for subsequent infusion: diphenhydramine 50 mg or equivalent, and/or acetaminophen 325-1000 mg, at least 30 minutes prior to SHR-1210 administration)	Continue

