5.4.3. Adverse events

AEs will be classified by treatment stage (before and after study treatment).

All AEs will be coded using MedDRA V24.0 and graded using NCI-CTCAE v4.03. Subject will be counted only once, even if the subject experiences more than one event within the same system organ class (SOC) and/or preferred term (PT). For the same AE reported in one subject multiple times but varying in CTCAE grade, the highest grade will be counted.

AEs will be ordered by descending incidence of SOC, and by descending incidence of PT within each SOC. If the incidence of ≥ 2 PTs is equal, the AEs will be ordered alphabetically. If there is no AE under a SOC or PT, the analysis will not be conducted.

Only TEAEs will be summarized. All AEs will be listed. AEs with completely missing onset time will be treated as TEAEs.

For AEs occurring after the start of study treatment, treatment-related AEs include those whose causality with the study drug is related, possibly related, or unassessable; if the causality assessment is missing, then the AE will be deemed treatment-related for analysis. AEs with any missing CTCAE grade will be analyzed based on the highest grade.

In AE summary table, AEs after study drug treatment will be analyzed according to the population/cohort, and the frequency and proportion will be used for statistical description. Analyses of AEs include but are not limited to the following:

- Any TEAE
- Treatment-related TEAE
- Any treatment-emergent serious adverse event (TESAE)
- Treatment-related TESAE
- CTCAE Grade ≥ 3 TEAE
- CTCAE Grade ≥ 3 treatment-related TEAEs
- Any TEAE with an incidence of $\geq 5\%$
- Treatment-related TEAE with an incidence of $\geq 5\%$
- AEs leading to treatment discontinuation
- Treatment-related AEs leading to treatment discontinuation
- AEs leading to discontinuation of SHR-1210
- Treatment-related AEs leading to discontinuation of SHR-1210
- AEs leading to discontinuation of apatinib
- Treatment-related AEs leading to discontinuation of apatinib
- AEs leading to interruption of SHR-1210
- Treatment-related AEs leading to interruption of SHR-1210
- AEs leading to interruption of apatinib
- Treatment-related AEs leading to interruption of apatinib
- AEs leading to dose reduction of apatinib
- Treatment-related AEs leading to dose reduction of apatinib
- AEs leading to death
- Treatment-related AEs leading to death
- TEAEs of special interest (SIEs, see Appendix 2 for specific classification)

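### SAP Appendix 2 is narrower than the special-interest categories it classifies, so, applied as written, it would undercount Grade ≥ 3 infusion reactions and Grade ≥ 3 irAEs in that table

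*SAP*

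**What the plan says.** SAP 5.4.3 includes among its adverse-event summaries "TEAEs of special interest (SIEs, see Appendix 2 for specific classification"). It then names the categories. Two matter here, infusion reactions of Grade ≥ 3 and other irAEs of Grade ≥ 3, and neither is limited by organ or term. Protocol 8.5 defines the same two categories with the same openness.

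Appendix 2 is titled "List of Preferred Terms for Special Interest Events". Under the infusion category it has one term, "Infusion related reaction". Under other Grade ≥ 3 irAEs it has four: "Immune-mediated lung disease", pneumonitis, "Immune-mediated hepatitis" and "Hepatic function abnormal". The SAP does not say whether the list is exhaustive or illustrative, and it gives no rule for a term that is not on it.

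Protocol 9.2 sets the scope of infusion reactions more widely: "For acute infusion reactions (including cytokine release syndrome, angioedema, anaphylactic shock, allergic reactions" and so on. Protocol 8.7 describes irAEs of the lung, bowel, liver, thyroid, kidney and pituitary, plus a residual class. The footnote to its Table 8-2 foresees Grade 3 skin and endocrine events.

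**The concern.** A preferred-term list turns a clinical category into something that can be programmed. If it is narrower than the category, the table carries a heading that its contents do not match. A reader who sees no Grade ≥ 3 infusion reaction beyond the listed term, or no other Grade ≥ 3 irAE outside lung and liver, could take that as a finding about the combination when it only reflects the list.

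The list can also err the other way. Two of its terms, eye pain (under uveitis) and "Hepatic function abnormal" (under other Grade ≥ 3 irAEs), are not specific to the category they stand for.

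At stake is the internal validity of one safety table. These are the categories that Protocol 8.5 asks sites to report to the sponsor within 24 h, so readers will expect the table to match them.

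**Working it through.** No figure in the plan needs reproducing. The check compares the list with the definitions.

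**1. Count the Appendix 2 rows.** Amylase or lipase 2, reactive capillary endothelial proliferation 1, infusion reaction 1, diarrhea/colitis 5, uveitis 2, interstitial pneumonia 1, hepatic enzyme abnormal 1, other Grade ≥ 3 irAEs 4. Total: 2 + 1 + 1 + 5 + 2 + 1 + 1 + 4 = 17. No row names anaphylaxis, cytokine release, angioedema or hypersensitivity, or a thyroid, renal, pituitary or skin immune event.

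**2. Set scope against list.**

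| Category | Scope in the documents | Terms in Appendix 2 |
|---|---|---|
| Grade ≥ 3 infusion reaction | Open in SAP 5.4.3 and Protocol 8.5; Protocol 9.2 includes cytokine release syndrome, angioedema, anaphylactic shock, allergic reactions | 1 |
| Other Grade ≥ 3 irAEs | Open in SAP 5.4.3 and Protocol 8.5; Protocol 8.7 names thyroid, renal and pituitary as well as lung, bowel and liver | 4 (2 lung, 2 liver) |

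**3. Run example events through the list, matching by term.**
- Grade 3 anaphylaxis during an infusion, coded under its own term: inside the category by Protocol 9.2, no match.
- Grade 3 immune-related hypothyroidism, nephritis or hypophysitis: inside the category by Protocol 8.7, no match.
- Grade 3 abnormal hepatic function caused by liver metastases: outside the category, because Protocol 8.7 requires tumor and other causes to be ruled out, yet it matches. Protocol 1.7.2.1 also reports raised bilirubin and transaminases as reactions to apatinib alone.
- Grade 2 eye pain from another cause: not uveitis, yet it matches the uveitis row.

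The first two undercount and the last two overcount.

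**4. Where else the missed events appear.** SAP 5.4.3 separately tabulates Grade ≥ 3 TEAEs, treatment-related Grade ≥ 3 TEAEs and irAEs, and lists all AEs. A missed event drops out of the special-interest table only.

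**5. Can the Phase I data give a size?** Protocol 1.7.1 shows one Grade ≥ 3 hypothyroidism among 87 subjects in China, 1/87 = 1.1%. Applied to 174 Stage II subjects:
- expected cases: 174 × 1/87 = 2.0
- chance of at least one: 1 − (86/87)^174 = 0.87
- exact 95% CI for 1/87: about 0.03% to 6.2%, so the chance of at least one runs from about 5% to nearly 100%.

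One event gives no usable rate.

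**The case against.** The strongest reply is that Appendix 2 is never said to be exhaustive or to override SAP 5.4.3, whose category headings stay open. Protocol 8.5 has investigators report special-interest events on a dedicated form, and the SAP does not say that the term list supersedes that report. A reaction during infusion may also be coded to "Infusion related reaction", depending on the term reported. All this stands as far as it goes, and it rules out any claim that these events could never be counted. It does not remove the problem. Appendix 2 is the only classification source that the SAP cites. If it is merely illustrative, the SAP has no rule for the remaining events, and coding that depends on the reported wording is not a rule either.

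A second reply is that nothing is lost and no decision rests on this table. That is correct and limits the importance of the point.

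A third concerns Protocol 13.4.4, which says "immune-related thyroid dysfunction, immune-related nephritis and renal failure, and immune-related hypophysitis will be categorized and summarized". A reader might infer that Appendix 2 breaches it. It does not: that section governs the irAE summary, which the SAP provides separately. The mismatch here is with SAP 5.4.3 and Protocol 8.5, 8.7 and 9.2.

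Finally, "Hepatic function abnormal" already sits under an irAE heading, so counting it by term alone is an assumption about programming, and Protocol 8.5 sets no immune-causality condition for uveitis. Both points stand, and the change proposed for those terms respects them.

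**Conclusion.** The point holds. If Appendix 2 is applied as the classification list, the special-interest table would undercount Grade ≥ 3 infusion reactions and Grade ≥ 3 irAEs against the SAP's own headings, and two non-specific terms could overcount. This assumes that programmers match terms to the list, which is the natural reading of SAP 5.4.3. It also assumes that the list is complete as shown; it closes the SAP, and nothing signals a continuation.

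Two stronger inferences are not supported.
- A reader might conclude that about two cases of Grade ≥ 3 hypothyroidism would probably be missed. Besides the width of the interval, the Phase I table covers AEs of any cause, and the highlighting that marks treatment-related events cannot be read. Grade ≥ 3 treatment-related AEs were 2.3% in all (2/87), and nothing shows that the hypothyroidism was related, still less immune-related. The data come from SHR-1210 alone in mixed tumors.
- A reader might cite the one treatment-related anaphylaxis in Phase I as an event that the list would miss. The companion table of Grade ≥ 3 AEs, from the same studies and data cut, shows no anaphylaxis and no immune-system class. The case was apparently below Grade 3 and would not qualify under any list.

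The consequence is therefore a mislabeled table of unknown but probably small numerical effect, cheap to correct before database lock.

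**What to change.** Revise Appendix 2 as follows.

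1. **Grade ≥ 3 infusion reaction.** Add terms for the conditions that Protocol 9.2 names (cytokine release syndrome, angioedema, anaphylactic reaction or shock, hypersensitivity), counted when onset is during or within 24 h of an SHR-1210 infusion. Protocol 8.6 gives 24 h as the period when allergic reactions are most likely.
2. **Other Grade ≥ 3 irAEs.** Replace the four terms with a definition: every Grade ≥ 3 event identified as an irAE for the SAP 5.4.3 irAE table and not already counted in another special-interest row, grouped by organ class. The exclusion prevents double counting of immune colitis, uveitis and interstitial pneumonitis, which have their own rows. The SAP should state who identifies irAEs, since it gives no rule now.
3. **Non-specific terms.** Count "Hepatic function abnormal" in that category only when the event is identified as an irAE. Count eye pain as uveitis only when the record supports uveitis.

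The cost is appendix wording and the reprogramming of one table. Special-interest counts may change slightly, in either direction.
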